5.4 Conditions for Storage and Use

The investigator will ensure that the IMP will be stored under appropriate conditions in a secure location with controlled access. The IMP should be stored refrigerated (2°C to 8°C) (36°F to 46°F, Do not freeze) until dispensed to the maternal subject. The storage compartment shall be monitored regularly and the temperature shall be documented. Deviations in storage temperature must be reported to the sponsor as instructed in the IMP guideline.

After dispensing the IMP to the maternal subject, the IMP can be stored under refrigeration or at room temperature over the course of the treatment period. Prior to initial use, the nasal spray should

be primed according to instructions provided with the product. The trial center staff will prime all nasal spray bottles of IMP prior to weighing and dispensing to the subject.

5.5 Blinding/Unblinding

5.5.1 Blinding

This trial is a double-blind design in which the investigators and the maternal subjects will be blinded to treatment allocation throughout the trial.

The IMP will be packaged according to a computer-generated randomization list prepared for all trial centers. Merotocin and placebo nasal spray will be indistinguishable with identical appearance. The Ferring Global Biometrics Department will store the randomization list according to Ferring's standard operating procedures. Maternal subject randomization numbers will be linked to IMP numbers via treatment codes. The randomization list will not be available to any person involved in the conduct and evaluation of the trial until the trial database is released to the statistician. All staff at each trial center including the trial medication delegates will be blinded to treatment allocation throughout the trial.

Ferring personnel at the Bioanalysis Department analyzing blood and milk samples for merotocin will be blinded to treatment allocation when performing the analyses. The rest of the Ferring clinical trial team will be blinded to individual and group treatment allocation until after database lock, except for Safety Committee members who may be unblinded to the group treatment allocation under special circumstances. DMC members will have access to unblinded interim data to assess the futility at the interim analysis and will keep the data and analyses confidential.

5.5.2 Unblinding of Individual Subject Treatment

An emergency procedure will be available to the investigator and designated persons at Ferring through the e-CRF. Breaking of the blind for individual subjects in emergency situations can be required in case of a suspected unexpected serious adverse reaction (SUSAR), in case of an important AE where the knowledge of the IMP in question is required for therapeutic decisions for the management of the maternal subject, or in case a quantifiable amount of merotocin in the milk (see Section 3.5).

As far as the emergency permits, the need to break the blind will be agreed by the investigator and Ferring. If the event requires immediate unblinding by the investigator, the sponsor must be informed of the unblinding as soon as possible and be provided with the rationale for unblinding.

The investigator who unblinds a maternal subject's treatment will use the e-CRF and is required to enter a password and record the reason for unblinding before the treatment code can be broken. The e-CRF records when and by whom the code is broken. The investigator must record the event of

unblinding in the maternal subject's medical record, including the reason for unblinding, but not the treatment allocation if this can be avoided.

Under special circumstances (Section 3.5), the treatment allocation will be unblinded on an individual level by an ad hoc safety group, consisting of an independent GPV representative, an independent statistician and an external neonatology expert other than the expert in the Safety Committee.

If Ferring needs to unblind a maternal subject's treatment, the e-CRF will be used for unblinding. It is required to enter a password and record the reason for unblinding before the treatment code can be broken. The e-CRF records also when and by whom the code is broken. The code break will occur according to corporate operational procedures for unplanned unblinding of trial subjects. It may be necessary to unblind an individual maternal subject's treatment for the purposes of expedited reporting to the authorities or IRBs. In that situation, every effort will be made to maintain blinding of Ferring personnel involved in data analysis and interpretation. Other personnel may be unblinded for SUSARs, including trial center staff as well as staff acting on behalf of Ferring.

Information on whether the blind has been broken for any maternal subjects is available in the e-CRF and must be collected before the database is declared clean, locked, and released to the statistician.

In case the e-CRF cannot be accessed by the investigator, and hence the emergency unblinding cannot be performed within the e-CRF system, the investigator should contact Ferring Pharmacovigilance using the contact details below:

Ferring Pharmacovigilance

US Toll-free number: [REDACTED]

If Ferring Pharmacovigilance cannot access the e-CRF, a back-up procedure involving the e-CRF vendor is in place.

5.6 Dispensing and Accountability, Return and Destruction

The IMP must only be dispensed to subjects who meet the eligibility criteria and are randomized in this trial. The delegated trial staff will use an interactive response technology (IRT) system to assign and dispense IMP kits per the randomization performed within the e-CRF. The delegated trial staff will also record the dates and quantities dispensed to and returned by each subject, as well as manage the overall drug accountability for each subject within the IRT system. The trial staff will be blinded to treatment allocation throughout the trial.

The monitor will verify drug accountability of IMP throughout the trial and will document any discrepancies. All dispensed IMP will be returned by maternal subjects for drug accountability.

Concerning destruction, the delegated trial staff must ensure destruction of dispensed IMP in accordance with local legislation after drug accountability has been verified by the monitor within the IRT system, while non-dispensed IMP will be returned for destruction as instructed by the Ferring Clinical Trial Supply Department.

5.7 Auxiliary Supplies

Ferring will be responsible for providing every maternal subject with a multi-user, electric, double-pumping breast pump, a breast pumping kit (with connectors and other necessities), a cooler set, weighing scale(s) with a carrying case (if applicable), breast shields, containers, labels, weighing worksheet (if applicable), scales for weighing milk and infant (if applicable) and a supplementary kit. Ferring will also ensure the trial centers receive sufficient amount of all auxiliary supplies for the maternal subjects.

6 TRIAL PROCEDURES

Before performing any trial procedures, consent for potential maternal subjects and infants will be obtained. The investigator must address all questions raised by the parent participants and a copy of the signed and dated informed consent form(s) will be provided to the maternal subjects and their partners (as applicable).

This trial will consist of the following:

- A screening period starting when informed consent has been obtained and ending at randomization between 96 to 192 (+4) hours of delivery; the screening period must have an observation period of a minimum of 48 hours for the collection of milk expression data.
- A treatment period of 14 days, including a Day 3 visit, a Day 10 visit and a Day 15/End-of-Treatment visit. These visits can be postponed for a maximum of 2 days. In this trial, treatment days start from the time of randomization, with Day 1 being the first 24 hours after randomization, Day 2 being 24 to 48 hours after randomization, and so on. The treatment period will include 14 such consecutive intervals of 24 hours from the time of randomization, corresponding to 14 treatment days (Days 1 to 14). Trial visits can be scheduled according to calendar days without considering 24-hour periods. Maternal subjects should stop the administration of IMP as soon as having completed 14 days' treatment, rather than continue dosing until the Day 15/End-of-Treatment visit.
- A post-treatment follow-up period with a Follow-up visit on Day 18 for all maternal subjects who complete the assigned treatment of Days 1 to 14 or a Follow-up visit 3 days after the End-of-Treatment visit in case of premature discontinuation. The visit can be postponed for a maximum of 2 days.

No specific trial procedures are required for the infant.

6.1 Trial Flow Chart

Maternal subjects will undergo the procedures at the time points specified in the schedule of events as shown in [Table 3](#). Infants will undergo the procedures at the time points specified in the schedule of events as shown in [Table 4](#).

Table 3 Trial Flow Chart – Mother-related Activities

Procedure	Screening Visit ^a 0-144 hours of delivery	Randomization Visit 96-192 (+4) hours of delivery	Treatment			Follow-up Day 18 ^b /Follow-up Visit
			Day 3 Visit ^b	Day 10 Visit ^b	Day 15 ^b /End-of-Treatment Visit	
Written informed consent	X					
Inclusion/exclusion criteria	X	X ^c				
Demographics	X					
Medical history	X					
Obstetric history ^d	X					
Lactation history ^e	X					
Antenatal and peripartum history ^f	X					
Pre-pregnancy BMI	X					
Instructions and support for providing MoM	X.....					X
Breast pump and data collection instructions	X					
Record weights of milk ^g	X.....	X ^c				X
Dosing (as applicable) and milk expression documentation review	X.....	X ^c				X
Physical examination		X ^c			X	
Vital signs		X ^c	X	X	X	
Blood sampling (safety parameters)	X				X	
Randomization		X				
IMP dispensing and weighing		X	X	X		
IMP administration at trial center		X ^h	X ^h	X ^h		
Milk expression at trial center	X	X ^c , X ⁱ	X	X		
Milk sampling for merotocin concentration ^j			X	X		
Milk sampling for milk composition ^k		X ^c	X	X		
Blood sampling (PK) ^l			X	X		
Drug accountability			X	X	X	
Concomitant medications	X	X	X	X	X	X
Adverse events	X	X	X	X	X	X
End-of-Trial form ^m						X

a Screening period runs from the signing of informed consent to randomization and includes an observation period of a minimum of 48 hours. Maternal subject-related activities may be performed at more than 1 screening visit.

b Day 3, Day 10, Day 15/End-of-Treatment and Day 18/Follow-up visits can be postponed a maximum of 2 days. The maternal subjects should stop the administration of IMP as soon as having completed 14 days' treatment, rather than continue dosing until the Day 15/End-of-Treatment visit.

c Performed before randomization.

d Including parity and pregnancy outcomes.

e Including number and duration of lactation following previous deliveries (if any) and lactation data from the current postpartum period (number of milk expression sessions, timing of the first milk expression attempt, occurrence of skin-to-skin contact, and use of hand expression).

f Including gestational age, time and method of delivery, reason for preterm delivery, other pregnancy complications, presence of fetal growth restriction, birth weight, spontaneous or induced labor, use of antenatal steroids, and any use of oxytocin postpartum.

g Milk weights are to be recorded for all containers brought to sites during unscheduled and scheduled visits in accordance with instructions provided in the milk weighing procedures manual. Should breastfeeding occur, the amount of breastfed milk is established by weighing the infant before and after the breastfeeding has been completed by following standardized weighing instructions and by using a standardized scale.

- h IMP should be administered approximately 5 to 10 minutes before a milk expression session. IMP administration at sites at Day 3 and Day 10 visits for PK sampling should occur a minimum of 3 hours after the previous dose.
- i Two milk expression sessions are to be performed at the site at randomization: one prior to randomization, the other after IMP administration.
- j At Day 3 and Day 10 visit, a milk sample will be taken from milk expressed at the trial center for analysis of merotocin concentration in the milk. Samples are taken only if milk production is, at the discretion of the investigator, adequate to meet the needs of the infant.
- k At randomization, a milk sample will be taken from milk expressed at the trial center prior to randomization for milk composition analysis. At Day 3 and Day 10 visits, milk samples will be taken from milk expressed at the trial center. Samples are taken only if milk production is, at the discretion of the investigator, adequate to meet the needs of the infant.
- l Seven PK samples for measurement of merotocin concentration will be collected at Day 3 and Day 10 visits using an indwelling catheter at the following time points: pre-dose, 5, 10, 20, 30, 45, and 60 minutes after dosing in a minimum of 20 maternal subjects.
- m End-of-Trial form should be completed at the subject's last scheduled visit or at the time of premature discontinuation.

Abbreviations: BMI=body mass index, IMP=investigational medicinal product, MoM=mother's own milk, PK=pharmacokinetic

Table 4 Trial Flow Chart – Infant-related Activities

Procedure	Screening Visit 0-144 hours of delivery	Randomization Visit 96-192 (+4) hours of delivery	Treatment			Post-treatment Follow-up	Post-trial Activities		
			Day 3 Visit ^a	Day 10 Visit ^a	Day 15 ^a /End-of-Treatment Visit		Day 18 ^a /Follow-up Visit	At infant's discharge from NICU	One month after NICU discharge
Exclusion criteria		X ^b							
Collecting the following data from hospital records									
Medical history	X ^c								
Body weight		X ^d	X ^d	X ^d	X ^d		X		
Length and head circumference							X		
Concomitant medications ^e	X	X	X	X	X	X	X		
Adverse events ^e	X	X	X	X	X	X	X		
Morbidity events of special interest ^f	X	X	X	X	X	X	X		
Infant enteral feeds			X ^g	X ^g	X ^g		X ^h		
Collection of additional NICU data							X ^h		
Collecting the following data by phone or other means									
Hospital re-admission and reason								X	
Administration of ASQ-3									X ⁱ

a Day 3, Day 10, Day 15/End-of-Treatment and Day 18/Follow-up visits can be postponed a maximum of 2 days.

b These assessments may be performed 0 to 144 hours of delivery but must be performed prior to randomization.

c Medical history for the infant refers to congenital conditions and events occurring from birth to signing of informed consent by the maternal subject. Events that occur following signing of informed consent are recorded as adverse events.

d Collected for all days from Day 1 to Day 14 as available from hospital records.

e Collected from hospital records from signing of informed consent through time of infant's discharge from NICU or until the last milk sample expressed during maternal subject's treatment with IMP is either consumed by the infant or discarded, whichever occurs last.

f Collected from hospital records from signing of informed consent through infant's discharge from NICU.

g Infant enteral feeds including volume of MoM and formula/donor milk fed to the infant as available from hospital records from Day 1 to Day 14.

h Including time to full enteral feeds, time to infant's discharge from NICU, number of days the infant requires TPN until

discharge from NICU, type of feeding (MoM and formula/donor milk) at time of infant's discharge from NICU, whether maternal subject is lactating at time of infant's discharge from NICU.

i Completion of the ASQ-3 by a primary caregiver at infants' 9 months, 18 months and 24 months of corrected gestational age.

Abbreviations: ASQ-3=Ages and Stages Questionnaire-3, MoM=mother's own milk, NICU=neonatal intensive care unit, TPN=total parenteral nutrition

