All maternal subjects who complete the assigned treatment of Days 1 to 14 will be asked to continue daily recordings of milk expression through the end of Day 17. The recordings and the expressed milk will be collected at the Day 18/Follow-up visit to document the volume of milk produced during the post-treatment follow-up period.

No specific trial procedures are required for infants. All infant data are based on hospital records. Infant body weight and infant enteral feeds (volume of MoM and formula/donor milk fed to the infant) will be collected from hospital records for all days as available from Day 1 to Day 14. Concomitant medications and AEs including morbidity events of special interest (NEC, intra-ventricular hemorrhage, BPD, RDS, late-onset sepsis, ROP, and hemodynamically significant patent *ductus arteriosus*) will be collected from hospital records from signing of informed consent. See Section 6 for further details.

Milk Expression Procedures

Maternal subjects will attempt to express milk with a multi-user, electric, double-pumping breast pump (Medela Symphony, Medela Inc., McHenry, Illinois) at least 5 times every 24 hours during the observation period and 6 to 8 times every 24 hours during the treatment and post-treatment follow-up periods, including at least once during the night and with no more than 5 hours between milk expression sessions. Both breasts should be pumped and emptied in accordance with the instructions provided in the lactation manual for subjects. Maternal subjects will also receive instructions on hand expression and hands-on pumping; use of the two methods is at subject's own

choice. All maternal subjects will receive detailed and standardized lactation instructions and expert lactation support. Steps will be taken to standardize best supportive care across trial centers.

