The fed volumes of MoM and of other enteral feedings (formula/donor milk) will be recorded by trial center staff based on the hospital records. It is expected that the majority of the infants will be hospitalized for the predominant or entire duration of the trial due to their prematurity. If the infant is discharged prior to the Day 18/Follow-up visit, the maternal subject will be instructed to continue to use the trial medication as planned and continue to record milk expression as instructed in the lactation manual for subjects and milk weighing procedures manual. Two standardized scales will be offered to the maternal subject for the recording of milk expression at home, one for measuring the weight of the expressed milk and one for measuring the weight of the infant before and after feeds (if the subject is breastfeeding).

Post-trial Activities

As part of post-trial activities after the Day18/Follow-up visit, infant AEs and concomitant

medications will continue to be collected from hospital records through infant's discharge from NICU or until the last milk sample expressed during maternal subject's treatment with IMP is either consumed by the infant or discarded, whichever occurs last. Information on infant's morbidity events of special interest is collected through infant's discharge from NICU based on hospital records.

In addition, the following data will be collected from the hospital records as available when the infant is discharged from NICU: infant body weight, length and head circumference at time of discharge from NICU, time to full enteral feeds, time to discharge from NICU, number of days the infant requires TPN until discharge from NICU, type of feeding (MoM and formula/donor milk) at time of discharge from NICU, and whether the maternal subject is lactating at time of infant's discharge from NICU.

A further post-trial activity is to establish a contact with the maternal subject (by phone or other means) about one month after the infant's NICU discharge to inquire about any hospital re-admission of the infant and the reason for such.

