6.6.2 Infant-related Activities about One Month after NICU Discharge

- Contact the maternal subject, by phone or other means, to establish whether the infant has been re-admitted to hospital since the NICU discharge and, if so, the reason for the re-admission

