8 ADVERSE EVENTS

8.1 Adverse Event Definition

An AE is any untoward medical occurrence in a subject participating in a clinical trial. It includes:

- Any unfavorable and unintended sign, symptom or disease temporally associated with the use of the IMP, whether or not considered to be caused by the IMP
- AEs commonly observed and AEs anticipated based on the pharmacological effect of the IMP
- Any laboratory abnormality, vital sign or finding from physical examination assessed as clinically significant by the investigator [note: findings from assessments and examinations done during screening are not AEs but are recorded as medical history]
- Accidental injuries, reasons for any change in medication (drug and/or dose), reasons for any medical, nursing or pharmacy consultation or reasons for admission to hospital or surgical procedures

Overdoses, medication errors and technical malfunctions of IMP will be captured by the e-CRF and will be reviewed by Ferring Pharmacovigilance on an ongoing basis.

Pre-treatment Adverse Event for Maternal Subjects

A pre-treatment AE for a maternal subject is any untoward medical occurrence arising or observed between informed consent and administration of the IMP.

Treatment-emergent Adverse Event for Maternal Subjects

A TEAE for a maternal subject is any AE occurring after start of the IMP and before the Day 15/End-of-Treatment visit. A pre-treatment AE or pre-existing medical condition that worsens in intensity after start of IMP and before the Day 15/End-of-Treatment visit is also considered treatment emergent.

Pre-treatment Adverse Event for Infants

A pre-treatment AE for an infant is any untoward medical occurrence arising or observed between the signing of the parental informed consent and the infant's first exposure to MoM expressed during maternal subject's treatment period.

Treatment-emergent Adverse Event for Infants

A TEAE for an infant is any AE occurring from the infant's first exposure to MoM expressed during maternal subject's treatment period until the infant's last exposure to MoM expressed during maternal subject's treatment period (i.e., the last milk sample expressed during maternal subject's treatment with IMP is either consumed by the infant or discarded). A pre-treatment AE or pre-existing medical condition that worsens in intensity during the interval stated above is also considered treatment emergent.

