8.2 Collection and Recording of Adverse Events

8.2.1 Collection of Adverse Events

The sources of AEs cover:

- The subject's response to questions about her health (a standard non-leading question such as 'How have you been feeling since your last visit?' is asked at each visit). (This is only applicable to maternal subjects)
- Symptoms spontaneously reported by the subject. (This is only applicable to maternal subjects)
- Investigations and examinations where the findings are assessed by the investigator to be clinically significant changes or abnormalities
- Other information relating to the subject's health becoming known to the investigator (e.g., hospitalization)

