8.2.4 Collection and Recording of Adverse Events for Infants

Events that occur in infants following the signing of parental consent are to be collected as AEs. Data regarding these AEs are to be recorded in the e-CRF using information obtained from the infant's hospital records (as available). Infant AEs will be collected and recorded from the time informed consent is obtained through the Day 18/Follow-up visit during the trial. As part of post-trial activities after the Day18/Follow-up visit, infant AEs will also be collected and recorded through time of infant's discharge from NICU or until the last milk sample expressed during maternal subject's treatment with IMP is either consumed by the infant or discarded, whichever occurs last. These AEs will be reported separately from those collected through the Day 18/Follow-up visit.

About one month after the infant's NICU discharge, the maternal subject will be contacted (by phone or other means) to inquire about any hospital re-admission and the reason for such.

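### The infant adverse event window can run past NICU discharge, but after discharge no active step collects events without a hospital record or dates the last treatment-period milk

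*Combined protocol and SAP*

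**What the plan says.** **Window.** Section 6.1 (Table 4, footnote e) has infant AEs "Collected from hospital records from signing of informed consent through time of infant's discharge from NICU or until the last milk sample" from the treatment period is consumed or discarded, taking the later of the two dates. Sections 3.1.2, 3.6.8, 6.6.1, 7.4 and 8.2.4 repeat this rule. Section 8.1 runs the infant TEAE period "until the infant's last exposure to MoM expressed during maternal subject's treatment period".

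**Source.** Section 3.1.2 states: "All infant data are based on hospital records". Section 8.2.4 names the same source for infant AEs and qualifies it by availability. Section 8.2.1 restricts the health question and spontaneous symptom reports to mothers.

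**After discharge.** Section 6.6.2 plans one contact with the mother about a month after NICU discharge, "to establish whether the infant has been re-admitted to hospital since the NICU discharge", and if so why.

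**Exposure at home.** Section 3.1.2 foresees discharge before the Day 18 visit, in which case "the maternal subject will be instructed to continue to use the trial medication as planned". Sections 6.4.3 and 7.1.1 supply scales for home use, and expressed milk is stored for later feeding.

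**The concern.** The window is defined by exposure to milk, while the data source is defined by where the infant is. The two coincide only while the infant is in hospital. An infant who goes home while the mother is still dosing, or with stored treatment-period milk, remains inside the TEAE window without routine observation.

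Frequency and intensity of infant AEs is a secondary endpoint (Section 2.2), and infant TEAEs are tabulated by system organ class and preferred term (Section 9.8.2). Section 1.3 describes this as the first trial with merotocin exposure beyond 45 hours. If merotocin is quantifiable in a milk sample, the ad hoc safety group reviews the infant data in the database and the hospital records (Section 4.4.2). A home event that reached neither would be absent from that review.

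**Working it through.** The plan gives no figure to reproduce. The check sets the texts side by side and adds one date calculation.

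**1. End of the window.** Let D be the date of NICU discharge and M the date the last treatment-period milk is fed or discarded. Collection ends at max(D, M); the TEAE period ends at M. The part of the TEAE period spent at home is max(0, M − D), which is positive whenever treatment-period milk is still in use after discharge.

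**2. Can M fall after D?** Yes, in two ways the protocol itself allows: discharge while the mother is still dosing, or discharge with stored milk still to be fed (Section 3.1.2).

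**3. How mature is the infant when dosing ends?** Age at end of dosing = gestational age at delivery + time to randomization + 14 days.
- Current upper limit, 34 weeks + 2 days: 34 × 7 + 2 = 240 days. Randomization at 96 to 196 hours is 4 to 8.2 days. End of dosing: 240 + 4 + 14 = 258 days to 240 + 8.2 + 14 = 262.2 days, about 36 weeks + 6 days to 37 weeks + 3 days.
- Original upper limit, 31 weeks + 6 days (Section 3.6.6), with randomization at 96 to 144 hours, or 4 to 6 days (Section 3.6.1): 223 + 4 + 14 = 241 days to 223 + 6 + 14 = 243 days, about 34 weeks + 3 days to 34 weeks + 5 days.

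The amendment thus makes the most mature infants 17 days (258 − 241) to about 19 days (262.2 − 243) older when dosing ends. That gives a direction only; the documents contain no discharge rate by age.

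**4. Which routes reach an infant AE at home between D and M?**

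| Route | Section | Reaches an event without re-admission? |
|---|---|---|
| Hospital records at visits and at discharge | 3.1.2, 6.4.2 to 6.6.1, 8.2.4 | Only if the event left a record the site can obtain |
| Health question at each visit | 8.2.1 | No, mothers only |
| Spontaneous report | 8.2.1 | No, mothers only |
| Other information reaching the investigator | 8.2.1 | Possibly, but nobody is asked to seek it |
| One-month contact | 6.6.2, 7.4, 8.2.4 | No, re-admission and its reason only |
| Serious AE learned of in long-term follow-up | 8.6.2 | Only if serious, judged possibly related, and known to the investigator |

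The mother attends on Days 15 and 18 and reports her own AEs. The infant AEs at those visits still come from hospital records (Sections 6.4.4 and 6.5.1).

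**5. Who records M?** None of the activity lists from Day 3 to the one-month contact (Sections 6.4.2 to 6.6.2) includes it. Section 6.6.1 is headed as an activity at discharge, yet asks for AEs up to M, which may lie in the future. The next contact does not ask for M.

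**6. Size.** The number affected is the number of infants with M after D. The documents give neither the distribution of discharge times nor how long stored milk lasts, so no count or range follows from them.

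**The case against.** The strongest reply is that record-based infant follow-up is a declared choice and that serious events are covered. Re-admissions and their reasons are obtained from the mother, assessed for causality (Section 7.4) and reported as serious AEs if possibly related (Section 8.6.2). Other information that becomes known to the investigator is an AE source not limited to mothers. Delivery must be within the trial center's hospital system (Section 4.1.1), and nothing says that access to records ends at NICU discharge. Infant AEs after Day 18 are reported separately (Sections 3.6.8 and 8.2.4). The protocol expects most infants to be in hospital for most or all of the trial. Merotocin in milk was below the limit of quantification in all subjects of the single-dose transfer trial (Section 1.2).

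Most of this stands, and it narrows the point. A reader might infer that every infant event after discharge is lost. The documents do not support that: re-admissions are sought, and events with a hospital record can be found. What the reply does not supply is an active route for an event with neither, or a way to date the last milk use. A site manual or the e-CRF might cover the date, but the protocol's activity lists do not. The expectation about hospital stay concerns the trial period and does not address milk stored and used later.

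A reader might also infer that under-reporting differs between arms, because merotocin is meant to raise milk volume and so perhaps stored milk. That is plausible but not shown. There is no figure for stored milk at discharge in either arm, and mothers enter producing under 200 mL a day, so a large surplus cannot be assumed.

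**Conclusion.** The point holds in a limited form. The infant AE and TEAE windows can outlast the hospital stay. In that interval, events without re-admission or another hospital record, which will mostly be non-serious, have only a passive route into the AE log. The end date of the TEAE window cannot be verified after discharge, so the treatment-emergent label on an event found later may be uncertain.

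The primary efficacy analysis is not touched. The effect is on the completeness of one secondary safety endpoint and its post-trial continuation. For infants discharged after Day 18, it falls only on AEs that are reported separately. The number of infants, the number of events and any imbalance between arms cannot be derived from the documents. The conclusion assumes that unseen manuals and e-CRF pages do not already ask for the last-milk date or for infant AEs at home.

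**What to change.** At the planned one-month contact, and at the Day 15 and Day 18 maternal visits if the infant is already home, ask the mother:

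1. On what date was the last treatment-period milk fed or discarded, or does some remain? If some remains, repeat the contact.
2. Has the infant had any AE between discharge and that date?

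Enter the answers in the e-CRF flagged as parent-reported, and tabulate them separately from record-based AEs so that the two sources are not mixed. Align Table 4 footnote e and Sections 6.6.1, 6.6.2, 8.1, 8.2.1 and 8.2.4 with this.

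The contact and the visits already exist, so the cost is the extra questions, an occasional repeat contact, and a full AE-log entry (onset, intensity, causality, outcome and seriousness, Section 8.2.2) for each event reported. Parent recall of minor events is less precise than a hospital record.

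If the sponsor prefers not to add this, the protocol should state that infant TEAEs after discharge are limited to hospital-recorded events and re-admissions, and the same sections should be aligned to say so.
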